5.1 Inclusion Criteria

Adult 18 years or older

Exclusion Criteria

- Women who are currently pregnant or breastfeeding
- Use of antibiotics within the last 2 weeks
- Use of supplementary vitamin D within the last month
- Self-reported, pre-existing history of inflammatory bowel disease, heart disease or diabetes
- Students under 18
- Tanning/sun exposure > 60 min at a time in last 4 weeks
- No phenobarbital, carbamazepine, spironolactone chronic therapy; or steroid use within the last 2 weeks
- Severe allergy to ingredients found in supplements

It might be possible that some students enrolled in BIO 1125 may be under the age of 18, however, these students will be excluded from study enrollment as we are only studying the effects on adults as part of this research.

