2.1 Relationship between Dietary Intake and the Microbiome

Aim 1: To elucidate the complex relationship between the diet and microbiome using longitudinal data and mathematical modeling.

The complex relationship between dietary intake and the microbiome, and the potential health implications of human exposure to microbial metabolites, are only beginning to be understood. It is well known that altered dietary intake can trigger rapid, although transient, changes in the composition of the microbiome in as little as 1 to 2 days. The biggest factors in determining microbial response to diet are thought to include an individual's starting microbiome, long-term dietary habits, and environmental exposures. However, there is some controversy over the extent to which long-term dietary patterns (i.e. vegan v. omnivore) influence the composition of the microbiome.

We still do not have a good understanding of how small dietary differences from day-to-day impact the microbiome. Recently the application of machine learning to a large dataset of microbiome, diet, anthropometrics, and blood test data was successfully used to predict blood glucose response to variable meal compositions. This finding suggests that personalized nutrition and optimal diets for health may be feasible in the future. A longitudinal dataset with accurately recorded dietary data and multiple samples over 12 weeks will provide valuable insight into the changes that occur at the individual level over time, while controlling for dietary trends and initial microbiome composition.

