2.2 Vitamin D Intervention

Aim 2: To identify shifts in the composition of the human microbiome and CRC risk factors specifically caused by the consumption of Vitamin D supplements.

IRB # 1845028-2 Version 3

Vitamin D is one of 4 fat-soluble vitamins that are only obtained from dietary or supplementary intake, and which is necessary for healthy immune function, bone metabolism and electrolyte absorption.⁸⁻¹¹ Since the 1980's intake vitamin D containing foods, milk, eggs, fish and mushrooms has been declining in the United States. 12 Most concerning has been the sharp decline in consumption of cow's milk, which is a primary source of vitamin D, particularly among young females. 13 Unfortunately, there has also been a sharp rise in EOCRC since 2000, from a rate of 5.9 cases/100,000 to 8.5 in 2018 (SEER). Projections for 2030 suggest 23% of rectal and 11% colon cancer will be diagnosed in US adults under the age of 50.14 Recently, however, a study using incident cases of EOCRC from the Nurses' Health Study II, demonstrated a 50% reduced risk of EOCRC from total dietary intake of vitamin D >/= 450 IU/day vs <300 IU/day (HR = 0.40, 95% CI, 0.26-0.93).¹⁵

Recent studies have determined the impact of habitual vitamin D intake and vitamin D supplementation on the human microbiome, and demonstrated beneficial modifications in composition. 16 Specifically, 12 weeks of weekly oral dose of 50,000 IU vitamin D₃ in 80 women increased the Bacteroides/Firmicutes ratio and increased probiotic bacteria Akkermansia and Bifidobacterium. 16 It is yet unclear mechanistically how Vitamin D alters the composition and function of the microbiome, but several lines of evidence indicate a bi-directional interaction. Indirect effects of Vitamin D on the microbiota include systemic effects through the vitamin D receptor (VDR), which is expressed not only in the proximal colon but also functions as a transcription factor in a large number of genes that control immune response. 17,18 Likewise. specific bacteria influence VDR expression in host cells. 19,20

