Study Visit Number	1							2								3	4	5
Study day (0-15)	0	1	2	3	4	5	6	7	8	9	10	11	12	13	14	15	16	17
Week of study	1	2						2							3			12
Decide if you want to participate	✓																	
Study training	✓																	
Study checkup								>								>	>	✓
Complete questionnaires	✓															√	✓	1
Measure body composition	✓															✓		✓
Collect stool		✓	1	✓	✓	✓	✓	✓	✓	✓	✓	✓	✓	✓	✓			✓
Record diet		✓	✓	✓	✓	✓	✓	✓	✓	✓	✓	✓	✓	✓	✓			1
Take dietary supplement		✓	√	✓	✓	√	✓	✓	✓	✓	1	✓	✓	1	✓	✓	✓	✓
Fasting blood draw	✓															✓		✓

Statistical Design and Microbiome Analysis 4

This longitudinal study will allow for the use of each subject as their own control. We will perform testing for associations between diet, taxa, groups of bacterial taxa (and their functional capacities) with metadata parameters in different combinations. We will test the null hypotheses that there are no associations between dietary intake variability and microbiome composition within and between subjects, and between dietary intervention groups. Finally, we will test the null hypothesis that vitamin D has no effect on the microbiome.

IRB # 1845028-2 Version 3 Date: March, 3 2022 **Primary Outcome:** Microbiome composition and the relationship with dietary and supplemental intake of vitamin D and serum vitamin D levels

Secondary Outcomes: Circulation inflammatory markers (e.g. TNFα, IL-8, CRP); markers of gut permeability (e.g. zonulin, intestinal fatty acid binding protein, soluble CD14, lipopolysaccharide and lipopolysaccharide-binding protein); glucose and insulin; and other nutritional and microbial metabolites.

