6.1 Demographics and Anthropometrics

At visit 1, basic demographic data will be collected including age, gender, race/ethnicity, and medication use. Participant weight will be measured to the nearest kg and height will be measured to the nearest cm at using an electronic scale and wall mounted tape-measure. Body composition will be measured using the InBody device, which is a bioelectrical impedance device that measures percent body fat and lean muscle, and has been used by [name] in other IRB approved studies at Baylor University. For students and study participants who have mental or physical issues where this would not be appropriate, such as a history of eating disorders, the option to just provide self-reported height and weight will be offered.

IRB # 1845028-2 Version 3 Date: March. 3 2022

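### For a microbiome primary outcome, the entry criteria allow antibiotics up to two weeks before entry and unlimited probiotic use, which adds avoidable noise with 20 per arm

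*Combined protocol and SAP*

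**What the plan says.** Section 4 gives the primary outcome as "Microbiome composition and the relationship with dietary and supplemental intake of vitamin D and serum vitamin D levels". It also states: "This longitudinal study will allow for the use of each subject as their own control".

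Two exclusions in section 5.1 bear on prior exposure: "Use of antibiotics within the last 2 weeks" and "Use of supplementary vitamin D within the last month". Neither window is justified. No criterion there, and no rule elsewhere, mentions probiotics, and section 7 does not deal with antibiotic or probiotic use during the 12 weeks.

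The background shows why the state of the microbiome at entry matters. Section 2.1 says: "The biggest factors in determining microbial response to diet are thought to include an individual's starting microbiome". Section 2.2 cites a 12-week vitamin D study that "increased the Bacteroides/Firmicutes ratio and increased probiotic bacteria Akkermansia and Bifidobacterium".

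Section 6.1 provides some capture at Visit 1: "basic demographic data will be collected including age, gender, race/ethnicity, and medication use". It does not name probiotics or the date of last antibiotic use. Section 4.1 matches participants on baseline vitamin D only. The outline and schedule in sections 3.1 and 3.2 start stool collection on study day 1, which is also the first day of gummies.

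**The concern.** Antibiotics and probiotics act on the primary outcome itself. A person just past two weeks from the last antibiotic dose is eligible, so the 14 daily stools may be collected while the community is still changing for reasons unrelated to diet or supplement. A person taking a Bifidobacterium product is eligible too and may stop or continue at will, which can move one of the genera cited in the rationale.

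Two kinds of analysis are affected differently. In the randomised comparison, the exposures add outcome variance and can fall unevenly by chance across two arms of 20. In the within-person analyses (the diet associations of Aim 1 and any own-control contrast), randomisation offers no protection, and drift within a person can be read as a response to diet or time. There is no stool from before the first gummy, so the data cannot show whether a participant was stable at entry.

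**Working it through.** **1. The plan's own figure.** Section 4.1 states a detectable change of 1.24 SD with 20 per arm, using a Mann-Whitney U test on lognormal taxa with Bonferroni correction over ten taxa. It does not state power, alpha or sidedness. Assume 80% power and two-sided alpha 0.05/10 = 0.005, with the SD on the log scale. Simulated power at 1.24 SD is 0.788 with exact p-values and 0.770 to 0.775 with the continuity-corrected normal approximation. The figure is reproduced on these assumptions, and it leaves no spare power.

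**2. How much antibiotic disturbance could remain.** The documents give no recovery time. Assume exponential decay with half-time h, so the fraction left on day t after the last dose is 0.5^(t/h). For someone two weeks past the last dose at Visit 1, study day 1 falls on about day 15, study day 14 on day 14 + 14 = 28, and the week-12 stool on about day 14 + 84 = 98.

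| Day after last dose | h = 7 days | h = 14 days | h = 28 days |
|---|---|---|---|
| 15 (first stool under the present rule) | 23% | 48% | 69% |
| 28 (fourteenth daily stool) | 6% | 25% | 50% |
| 98 (week-12 stool) | under 0.1% | 0.8% | 9% |
| 30 (about where a one-month window puts entry) | 5% | 23% | 48% |
| 90 (about where a three-month window puts entry) | about 0% | 1% | 11% |

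For example, 0.5^(15/14) = 0.476 and 0.5^(30/14) = 0.226. Within the 14 daily stools that feed Aim 1, the drop from day 15 to day 28 is 16, 23 or 19 points of the initial disturbance (22.6 − 6.3, 47.6 − 25.0, 69.0 − 50.0). From day 15 to week 12 it is 23, 47 or 60 points. This is the earliest eligible case, not the average participant.

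**3. What noise does to the between-arm test.** As an illustration with assumed values, let a share f of participants in both arms carry a displacement of s SD in a tested taxon, independent of arm. Power with no displacement, by the continuity-corrected test, is 0.775.

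| f | Power, s = 1 | Power, s = 2 | Chance of an imbalance of 3 or more |
|---|---|---|---|
| 5% | 0.74 | 0.69 to 0.70 | 7% |
| 10% | about 0.72 | 0.62 | 18% |
| 20% | 0.68 | about 0.50 | 32% |
| 30% | 0.66 | 0.40 to 0.41 | 39% |

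The last column takes two independent Binomial(20, f) counts and sums the probability that they differ by at least 3. The variance inflation is 1 + f(1 − f)s². At f = 10%, the n per arm needed to compensate is 20 × 1.09 = 21.8, so 22, for s = 1; and 20 × 1.36 = 27.2, so 28, for s = 2.

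**4. False positives.** With no vitamin D effect and s = 2, the rejection rate is 0.0038 at f = 10% and 0.0036 at f = 30%, against a nominal 0.005. Type I error is not inflated.

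**The case against.** The strongest reply is the placebo arm. A reader might infer that antibiotic recovery cannot be told apart from a 12-week supplement effect. The documents do not support that for the main comparison: section 4.1 randomises 20 against 20, and the power analysis uses a between-group test. Recovery can occur in either arm and separates from the supplement effect in that contrast. Nor is it right that the exposures are unbalanced. They are not matching factors, but randomisation balances them in expectation. What remains is noise and chance imbalance.

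If the test used only the week-12 stool, little antibiotic effect would be left: on the assumed half-times, at most 9% of the disturbance, or about 0.18 SD from a 2 SD displacement. That stands. The losses in step 3 therefore apply to the early stools, to a change measured from them, or to probiotic use that goes on. Section 4.1 does not say which stools enter the test.

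A reader might also infer that the trial expects vitamin D to raise Bifidobacterium. Section 2.2 reports this as the result of a cited study, section 4 tests a null of no effect without direction, and nothing places that genus among the ten dominant taxa. Likewise, the shorter antibiotic window is not a contradiction: the vitamin D window can serve a different purpose, protecting the exposure and the baseline level used for matching, and the steroid window is also two weeks.

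Partial mitigation exists. Medication use is recorded at Visit 1, diet is recorded on stool days, and section 4 plans tests against metadata parameters. None of these names probiotics or antibiotic dates, or commits to adjustment.

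**Conclusion.** The point holds as a low-cost improvement to eligibility and analysis. It does not show bias in the randomised comparison. Three facts rest on the documents alone: the outcome is the microbiome, the antibiotic window is two weeks without justification, and probiotics are not addressed. The likely harm is lost precision with 20 per arm, chance imbalance, and contamination of the within-person analyses, where no pre-dose stool helps.

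The size is uncertain. The decay form, the half-times, the exposed share and the displacement in SD are all assumptions. If few participants are exposed or recovery is fast, the loss is small (power 0.775 to 0.74 at 5% and 1 SD). At 10% and 2 SD it is material (0.62).

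**What to change.** In section 5.1:

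- Add an exclusion such as: *use of probiotic supplements within the last month, or unwilling to refrain during the study*. This matches the window already used for vitamin D.
- Lengthen the antibiotic window to at least the same month. A longer window, such as three months, is an option if recruitment allows. The documents do not fix a value, and on the 4-week half-time three months still leaves 11%.

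In section 6.1, record the dates of last antibiotic and probiotic use at Visit 1, and record any use during the 12 weeks.

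In section 4, prespecify a sensitivity analysis that repeats the between-arm and Aim 1 results without exposed participants. It should be read as supportive: dropping from 20 to 18 per arm lowers simulated power at 1.24 SD from 0.775 to 0.70, and excluding people for use after randomisation no longer rests on randomisation alone.

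The cost is a short amendment, a few screening and follow-up questions, and a few more screen failures or delayed entries. People outside a window can be screened again later. Under section 5.3, however, students consent before the course begins, so a delay may cost some of them their course cohort, and section 10 closes data collection in December 2022. Both favour one month as the minimum.

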4.1 Sample Size

We will enroll 40 adults in this study. The adults will be randomized, with 20 individuals per study arm, to receive either vitamin D (4000 IU daily) or placebo during the intervention period. To control for initial vitamin D (25(OH) D3) levels at baseline (including those with hypovitaminosis), subjects will be randomized using 1:1 matching based on vitamin provided from blood samples at study visit 1. Study PI will be blinded to subject randomization. We will obtain 15 stool samples and 15 24-hour dietary recalls from each individual, for a total of 561 stool samples and 561 dietary records. We will obtain pre- and post- intervention blood samples from each individual for a total of 81 blood samples. We performed a power analysis using vitamin D as the primary exposure, and the top 10 dominant microbial taxa as the primary outcome. Using monte carlo simulation of microbial taxa distributed according to a lognormal distribution, and a non-parametric Mann-Whitney U test for significant differentiation, we found that this sample size is sufficient to detect a change of ≥ 1.24 standard deviations in any one of the dominant taxa. This analysis accounted for multiple hypothesis testing using Bonferroni correction.

5 Participant Selection

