The recommended dose of vitamin D for adults is 600 IU/day and has an upper limit of 4000 IU/day, with clinical intervention to replete deficiency being 50,000I IU/day. We have set our dose at the upper daily limit, established by the Institute of Medicine, since this study is not mean to replete a clinical deficiency. The supplement will be provided as Nordic Naturals vitamin D3 gummies, which have been certified by a third party with Good Manufacturing Procedures. For these gummies, 4 gummies will provide 4000 IU of vitamin D3. Subjects will consume 4 gummies at the largest meal of the day for 12 weeks. Subjects who are assigned to the placebo group will be provided with placebo gummies, Yum Earth Organic Vegan Fruit Snacks, which have the same composition as the supplement but no vitamin D3. Both will be put in bottles without manufacture labeling so as to disguise the vitamin D from placebo. If for any reason we are not able to get these placebo products, we have the ability to print 3D molds and make our own placebo gummies, which we have done before in our food lab. See Table 1 for list of ingredients.

Table 1. Ingredients list of vitamin D3 and placebo supplements							
	Vitamin D	Placebo					
Ingredients	vitamin D (cholecalciferol)	Organic rice syrup					
	Organic tapioca syrup	Organic cane sugar					
	Organic cane sugar	Pectin					
	purified water	Citric Acid					
	pectin	Ascorbic Acid					
	citric acid	Natural flavors colored with					
		organic concentrate (Apple,					
		carrot,					
		pumpkin,blackcurrent)					
	furamic acid	Organic sunflower oil					
	natural flavor	Organic carnauba wax					
	sodium citrate dihydrate						
	fruit and vegetable juice (color)						
Allergens	Gluten Free	Vegan					
	Contains milk derivatives	Gluten Free					
	Non-GMO	Non-GMO					

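### The allergy exclusion reaches only undefined 'severe' allergy to ingredients, so a volunteer with a known non-severe milk allergy can be enrolled and given a vitamin D gummy declared to contain milk derivatives

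*Combined protocol and SAP*

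**What the plan says.** Section 5.1 has one criterion on allergy, in the exclusion list: "Severe allergy to ingredients found in supplements". It does not define the grade of allergy or name any allergen. No other criterion in the list concerns milk allergy or milk intolerance.

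Section 6.4 (Dietary Supplement Intervention) names the placebo as "Yum Earth Organic Vegan Fruit Snacks" and describes it as a product "which have the same composition as the supplement but no vitamin D3". Table 1 in the same section shows the two products side by side. In its Allergens rows the vitamin D column carries the entry "Contains milk derivatives"; the placebo column is marked vegan and has no milk entry. The ingredient rows of the vitamin D column name no milk item.

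On packaging, the section says: "Both will be put in bottles without manufacture labeling so as to disguise the vitamin D from placebo". On exposure: "Subjects will consume 4 gummies at the largest meal of the day for 12 weeks". If the named placebo cannot be obtained, the section says that "we have the ability to print 3D molds and make our own placebo gummies"; no ingredient list is given for that fallback.

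Section 4.1 gives the allocation: "The adults will be randomized, with 20 individuals per study arm".

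**The concern.** An exclusion criterion works only as site staff would apply it. Three features of this one, read with Table 1, leave a gap.

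- It stops at severe allergy, so a known milder milk allergy does not exclude a volunteer.
- It refers to ingredients, whereas milk appears in Table 1 only as a declared allergen.
- The text of Section 6.4 says the two products match apart from vitamin D3, so staff relying on that sentence would not expect a milk difference between the arms.

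Removing the manufacturer's labelling also takes away any allergen statement that the manufacturer printed, which might otherwise have caught the problem at home.

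What is at stake is a foreseeable and avoidable exposure in healthy adults, some of them students, who according to Section 9 gain no personal benefit. Section 8.2, on the safety of the supplement, covers manufacture, the upper intake limit and hypercalcemia but not allergens, so it does not close the gap.

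**Working it through.** The plan states no figure on this point, so there is none to reproduce. The check is a comparison of texts, followed by a rough scale.

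**Step 1: who is eligible.** Take a volunteer with a known, non-severe milk allergy. None of the criteria in Section 5.1 (pregnancy or breastfeeding, antibiotics, vitamin D use, listed diseases, age, sun exposure, listed drugs, severe allergy) excludes this person on that ground. The volunteer is eligible.

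**Step 2: what each arm supplies.**

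| | Vitamin D gummy | Named placebo |
|---|---|---|
| Milk item in the ingredient rows | none named | none named |
| Milk entry in the Allergens rows | yes | no; marked vegan |
| Manufacturer's labelling on the bottle | removed | removed |

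The study product brings milk derivatives to this volunteer only under allocation to vitamin D. Because the entry is not among the ingredients, a literal check of the criterion against the ingredient rows could overlook milk even for a severe allergy.

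**Step 3: internal consistency.** The statement that the products share one composition apart from vitamin D3 does not agree with Table 1, which shows differing ingredients as well as the differing milk entry.

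**Step 4: length of exposure.** 4 gummies × 7 days × 12 weeks = 336 gummies per vitamin D participant. This is not a milk dose: the documents give no quantity of milk derivative per gummy.

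**Step 5: scale.** Let p be the share of enrolled adults with a non-severe milk allergy. The documents do not give p, so the values below are assumptions. With n = 20 in the vitamin D arm and allocation unrelated to milk allergy:

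- expected number exposed = 20 × p
- chance of at least one = 1 − (1 − p)^20

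| Assumed p | Expected in vitamin D arm | Chance of at least one |
|---|---|---|
| 0.5% | 20 × 0.005 = 0.1 | 1 − 0.995^20 = 9.5% |
| 1% | 20 × 0.01 = 0.2 | 1 − 0.99^20 = 18.2% |
| 2% | 20 × 0.02 = 0.4 | 1 − 0.98^20 = 33.2% |
| 5% | 20 × 0.05 = 1.0 | 1 − 0.95^20 = 64.2% |

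**The case against.** The strongest reply is that the plan already has a product-specific allergy exclusion, prints the ingredients, and lets participants withdraw at any time (Section 7). The caption of Table 1 calls both products supplements, so the criterion can be read as covering both. How severe an allergy must be to keep a volunteer out is a clinical judgement. The consent pages are not in the review copy, so participants may be told about the milk content. Few people would be affected.

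Much of this stands. The criterion can be read to cover both products, disclosure at consent cannot be ruled out, and the numbers are small. None of it changes who is eligible under Section 5.1, or the fact that milk is declared in a part of the table to which the criterion does not refer.

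A reader might also infer more than the documents support:

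- *That any allergic reaction would point to the vitamin D arm.* It would not. The placebo has ingredients of its own that the vitamin D gummy does not list, such as rice syrup, sunflower oil and carnauba wax. A non-severe allergy to one of these is equally admissible and would be met only in the placebo arm.
- *That the gut-permeability and inflammatory markers would be biased.* The documents give no milk quantity and nothing to show that such an exposure shifts these secondary outcomes. Both arms also eat their normal diet, which may include dairy, so the difference concerns the study product and not total milk intake.
- *That the bottles carry no label.* The text removes the manufacturer's labelling only; a study label, even one with an allergen statement, is not excluded.
- *That the milk difference holds under every placebo.* It holds for the named one; the composition of the in-house fallback is not given.

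**Conclusion.** The point holds as a matter of participant safety and eligibility. As written, Section 5.1 admits a volunteer with a known non-severe milk allergy. Table 1 shows that this person would receive milk derivatives from the study product if allocated to vitamin D. The mismatch between an exclusion worded on ingredients and a milk entry made only under allergens means that screening could miss milk altogether.

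The expected scale is small: about 0.1 to 1 person in the vitamin D arm. That range rests on an assumed prevalence of 0.5% to 5% among those enrolled and on 20 participants in that arm. The severity of any reaction cannot be judged from the documents. The point does not affect power or the primary analysis. It is a cheap improvement worth making, not a threat to the trial's conclusions.

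**What to change.** Reconcile Section 5.1 with Section 6.4 and Table 1:

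1. Reword the exclusion so that it explicitly covers declared allergens as well as ingredients, for both study products, and names milk derivatives.
2. Ask about these items at screening, before randomisation.
3. Have the investigator and the IRB set and justify the allergy threshold, in place of the undefined grade now used. Whether milk intolerance should also exclude is part of that clinical decision and is not prejudged here.
4. Correct the statement in Section 6.4 that the two products share one composition, so that staff are not misled about milk.
5. If the in-house placebo is used, list its ingredients and check participants against them before it is dispensed.

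The cost is a short amendment, one screening question and perhaps a few additional exclusions from a target of 40.
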